4.5 Biochemical Islet Autoantibody Development

If a child develops two positive biochemical islet autoantibodies on or after the 12 month visit, the child and family will be asked to return within 1-2 months for a confirmatory blood test. If the same 2 autoantibodies are present at both visits, the child will be withdrawn from the study, and may be eligible to enroll in the TrialNet Natural History Study of the Development of Type 1 Diabetes.

4.6 Withdrawal from Treatment, Continued Follow-up

Analyses for this study will be conducted in accordance with the intent-to-treat principle. Once randomized into the study, a participant will undergo all scheduled follow-up assessments and will remain in the assigned treatment group until the end of follow-up or participation in the study, regardless of whether the mother or child is continuing to receive study substance. Withdrawal from the study and its scheduled follow-up assessments should only occur if the parent(s) withdraws consent or the infant develops two persistent positive autoantibodies which are

confirmed on or after the 12 month visit (see Section 4.5).

If the mother decides to discontinue treatment for her or her child for any reason, this will be documented on the appropriate form and the participant will be encouraged to continue with all scheduled follow-up visits. TrialNet research personnel will make every effort to keep mothers and children in the study even if the participant is no longer taking the study substance, or is not fully compliant with the treatment schedule. If a visit is missed, TrialNet research personnel will contact the participant to reschedule and encourage the participant to come back for their follow-up evaluations.

4.7 Re-entry into the Trial

Should the family decide to discontinue the study substance and not return for follow-up visits, the family will be encouraged to bring their child back for follow-up and can resume taking the study substance. If the parent(s) decides to bring their child back for follow-up assessments at a later date, he or she will be allowed and encouraged to do so.

5 Statistical Considerations

Analysis of study data will be conducted to address the primary objectives of the pilot feasibility trial, after all participants have completed the twelve-month visit. These objectives are stated in Section 1.2.3. An interim analysis will be conducted after 6 months of follow-up in the cohort for the Data and Safety Monitoring Board. Analyses will also be conducted to address other stated objectives, and other interrelationships among elements of study data of interest to the investigators and of relevance to the objectives of the study. Such analyses may also entail the use of data from other studies in combination with data from this study. Likewise, data from this study may be used in combination with data from another study to address objectives of that study. Analyses by gender and race/ethnicity, as appropriate, are also planned.

5.1 Statistical Analysis

The statistical analyses to be employed to address each of the study objectives are:

- 1. *Recruitment: Nine clinical sites will enroll an average of ten participants per site in one year (post approval by their IRBs).* The rate of accrual will be estimated using the mean rate from all sites, with a 95% confidence interval based on an underlying Poisson distribution [80].
- 2. Treatment Compliance: At least 90% of families will continue to take the study substance as instructed. The simple proportion of treatment compliance among all families and the 95% confidence limits will be computed.
- 3. *Visit Compliance: At least 95% of families will continue to attend follow-up visits.* The simple proportion of visit compliance among all families will be computed and the 95% confidence limits, separately for the month 6 and month 12 visits.
- 4. At least a 20% higher level of plasma and/or red blood cell membrane phospholipid DHA can be achieved in the experimental treatment group in comparison with the control group. The comparison between the two treatment arms will be based on a t-test of treatment effect in an Analysis of Covariance (ANCOVA) model adjusted for the baseline level of each measure [81].
- 5. At least a 20% lower level of the major inflammatory cytokine, IL1-beta, will be achieved in the experimental treatment group in comparison with the control group. The comparison between the two treatment arms will be based on a t-test of treatment effect in an Analysis of Covariance (ANCOVA) model adjusted for the baseline level of each measure [82].

All analyses will be stratified according to whether the participant was entered into the study prenatally (i.e. during pregnancy) or was entered after birth. This adjustment will be conducted using an additional factor in a regression model or through a stratified-adjusted analysis.

Families that contribute multiple participants to a treatment group require special methods. When possible, statistical methods that consider the family as the unit of analysis will be employed, in which all family members will contribute. Where such methods are not feasible, only the first participant entered from each family will be included in the analysis.

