3.4 Screening and Enrollment

3.4.1 Pregnant Women

Pregnant women may be referred to the study by their physician or recruited at participating TrialNet study sites. All sites will comply with HIPAA regulations. Screening will consist of a clinic visit to be conducted after the 24th week of gestation for the pregnant woman. The pregnant woman will be asked if she would be interested in participating in the research project. Those indicating interest will be referred to one of the Investigators or Study Coordinators for a description of the study. Essential components of the presentation are that the parent(s) are being invited to participate in research, participation in the study is voluntary, and participation may be ended at the parent(s)' request. TrialNet research personnel will provide the parent(s) with a full description of the study, the inclusion and exclusion criteria, the procedures involved, the study groups and the randomization process, time commitments and the schedule of follow-up visits. A screening data form will be completed.

Pregnant women without diabetes can be enrolled after screening with no laboratory tests required if they meet eligibility criteria. Pregnant women with diabetes will need an HbA1c test as part of eligibility screening prior to randomization.

Supplementation with the study substance (DHA or control) will begin immediately after randomization, and continue at least until the HLA type of the infant is known. At that time, infants will either be enrolled into the study as continuing infants and continue taking the study substance, or be deemed ineligible for continuation in the study. The consented mother will receive a TrialNet identification number, and a baseline data collection form will be completed. To determine HLA eligibility status for the infant, a sample will be obtained either at birth by cord blood collection, or by a heel stick collected 2 to 28 days after the birth.

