3.5 Group Assignment, Randomization, and Masking

After the parent(s) have signed the consent form, completed the screening visit(s), (i.e. met all of the inclusion criteria and none of the exclusion criteria), and completed the baseline procedures, the participant will be randomized to one of the two study groups: DHA study substance or control.

The Coordinating Center will specify a randomization schedule for the study sites. Participants will be randomized, in approximately equal numbers, to the two arms of the study. The randomization method will be stratified by TrialNet study site. This approach ensures that the treatment groups will be approximately balanced within each site.

In the event that multiple siblings are entered from a single family, only the first family member will count towards the recruitment goal of 90 participants. The treatment randomly assigned to the first family member will also be assigned to all other family members who enter. This is due to statistical considerations since family members do not represent independent observations.

The study will be double-masked, in that the participant and the clinical sites and personnel involved in participant care will be masked to the mother and infant's treatment group assignment. The Coordinating Center will maintain the list of participant randomization assignments.

Participants who do not meet all of the inclusion criteria or who have one of the exclusion criteria will not be eligible to continue in this study, but will be offered participation in another TrialNet study, if one is available.

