4.2.1.2 Infant Screening (Infant of Participating Pregnant Woman)

a. Day of Infant Delivery:

Specimen Tests (if cord blood available):

- HLA to determine eligibility
- Baseline islet autoantibodies, RBC fatty acid levels, inflammatory mediator levels, Vitamin D level and CRP level.
- Residual specimens for storage (if available)

b. Infant (2 to 28 days of age):

Informed Consent Process

Specimen Tests:

Infant:

If cord blood not collected at birth, blood is collected by heel stick for the following:

- HLA to determine eligibility
- Islet autoantibodies
- Residual specimens for storage (if available)

Mother:

- Islet autoantibodies
- Residual specimens for storage (if available)

Data Collection Procedures:

• Limited physical examination, pregnancy and birth history, medical history of infant, medication history, assessment of concomitant medications including vitamin and supplementation record, food frequency questionnaire, family history, and adverse events assessments.

4.2.1.3 Infant Enrollment (approximately 4 weeks after blood collected for HLA typing):

Other Procedures:

- Results of infant's HLA testing discussed with parent(s). Parents are only told if genes are higher or lower risk for type 1 diabetes.
- Authorization to release medical records related to birth
- Study capsules and/or formula collected/dispensed.

Mother Specimen Tests:

- RBC fatty acid levels, inflammatory mediator levels, Vitamin D level, and CRP
- If nursing, breast milk fatty acid levels
- Residual specimens for storage (if available)

Data Collection Procedures:

- Medical history, pregnancy history, birth history, a food frequency questionnaire, assessment of concomitant medications including vitamin and supplementation record, an immunization history, a food introduction history, and adverse events assessments.
- 4.2.2 Entry Point B: Screening After Birth (for mothers not enrolled during pregnancy)

4.2.2.1 Infant Screening (2 days to 5 months of age):

Informed Consent Process

Specimen Tests:

Infant:

- HLA to determine eligibility
- Islet autoantibodies
- Residual specimens for storage (if available)

Mother:

- Islet autoantibodies
- Residual specimens for storage (if available)

Data Collection Procedures:

 Limited physical examination, pregnancy and birth history, medical history of infant, medication history, assessment of concomitant medications including vitamin and supplementation record, food frequency questionnaire, and family history

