5.2 Sample Size Calculations

The sample size of 90 participants was selected based on the feasibility objective of the nine clinical sites recruiting an average of 10 participants in one year. The statistical properties of the study with this sample size to address each objective are:

Objective 1. A sample size of 90 participants would allow the estimation of the rate of accrual to within \pm 11.1%.

Objective 2. This sample size would allow the estimation of a treatment compliance of 0.90 with logit-based confidence limits of 0.819, 0.947.

Objective 3. This sample size would allow the estimation of visit compliance with logit-based confidence limits of 0.880, 0.980.

Objectives 4-5. This sample size will provide 85% power to detect a difference of 0.63 standard deviation units between groups with a test at the 0.05 level two-sided.

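### The ANCOVA for Objectives 4 and 5 needs a baseline that the schedule does not supply: no infant value before randomisation for postnatal entrants, and cord blood drawn after dosing began for prenatal entrants

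*Protocol*

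**What the plan says.** Protocol Section 5.1 tests both the DHA difference (Objective 4) and the IL1-beta difference (Objective 5) by a "t-test of treatment effect in an Analysis of Covariance (ANCOVA) model adjusted for the baseline level of each measure [81". The person whose baseline is meant is not named. The same section adds that "All analyses will be stratified according to whether the participant was entered into the study prenatally" or after birth.

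The sampling schedule gives the following for fatty acids and inflammatory mediators.

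- **Prenatal entry, mother.** Section 4.2.1.1 schedules a sample at her screening and enrolment, before the unborn infant is randomised.
- **Prenatal entry, infant.** Section 4.2.1.2 lists, on the day of delivery and if cord blood is available, "Baseline islet autoantibodies, RBC fatty acid levels, inflammatory mediator levels, Vitamin D level and CRP level". But Section 3.4.1 says "Supplementation with the study substance (DHA or control) will begin immediately after randomization", which is in the third trimester. If cord blood is missed, the replacement heel stick covers HLA, islet autoantibodies and storage only.
- **Postnatal entry, infant.** Section 4.2.2.1, "Infant Screening (2 days to 5 months of age"), provides HLA and islet autoantibodies only. Appendix B allots 0.5 cc to each and nothing to the other assays. The first infant fatty acid and mediator values come at the 6-month follow-up visit (Section 4.3.2).
- **Postnatal entry, mother.** Section 4.2.2.2 samples nursing mothers at the enrolment visit. Non-nursing mothers are not sampled for these assays.

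For Objectives 4 and 5, Section 5.2 claims "85% power to detect a difference of 0.63 standard deviation units between groups with a test at the 0.05 level two-sided".

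**The concern.** The infant is the randomised participant, and the 6- and 12-month blood levels are infant levels. The natural reading of the covariate is therefore the infant's own earlier value. On that reading the covariate is missing for the postnatal half. For the prenatal half it is an early outcome, because Section 2.2.3 itself reports that maternal supplementation raises fatty acid levels in umbilical plasma and DHA in the newborn's blood.

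Adjusting for a value that treatment has already moved subtracts the part of the effect achieved in utero. These two harms are not alternatives: on the infant reading with complete-case fitting they occur together. Objectives 4 and 5 are two of the five criteria for considering a full-scale trial (Sections 1.2.3 and 1.2.4), so a real rise in DHA could be reported as too small.

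**Working it through.** **Inputs from the documents.** 90 participants in about equal arms, so 45 per arm (Sections 3.5 and 3.7.1); about half entering by each route (Section 1.2.2), so about 45 prenatal infants, 22.5 per arm; difference 0.63 SD, two-sided 0.05 (Section 5.2).

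**Assumed, because the documents give no figure.** Within-arm correlation ρ between the covariate and the later value: 0.3, 0.5, 0.7. Treatment shift already present in cord blood, d_c: 0 (none), 0.315 SD (half the final effect) or 0.63 SD (all of it).

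**1. The plan's own figure.** The standard error of a difference in SD units is √(2/n) with n per arm. With n = 45: √(2/45) = 0.2108; 0.63/0.2108 = 2.988; 2.988 − 1.960 = 1.028; power = Φ(1.028) = 0.848. The noncentral t gives 0.840. The 85% is reproduced, for an unadjusted comparison of all 90.

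**2. Prenatal infants only, no gain from the covariate.** With n = 22.5: √(2/22.5) = 0.2981; 0.63/0.2981 = 2.113; 2.113 − 1.960 = 0.153; power = 0.561 (noncentral t 0.542). The difference detectable with 85% power is (1.960 + 1.036) × 0.2981 = 0.89 SD, against (1.960 + 1.036) × 0.2108 = 0.63 SD for all 90.

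**3. Prenatal infants only, adjusted for cord blood.** With equal SDs:

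- adjusted effect = 0.63 − ρ·d_c
- standard error = √[(1 − ρ²)(2/n)(1 + d_c²/4)]

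Example, ρ = 0.5 and d_c = 0.63: effect = 0.63 − 0.315 = 0.315; standard error = √(0.75 × 0.0889 × 1.099) = 0.271; ratio = 1.16; power on 42 degrees of freedom about 21%.

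Adjusted effect in SD, and power from the noncentral t with 42 degrees of freedom:

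| Cord shift d_c | ρ = 0.3 | ρ = 0.5 | ρ = 0.7 |
|---|---|---|---|
| 0 | 0.63; 58% | 0.63; 66% | 0.63; 82% |
| 0.315 SD | 0.54; 44% | 0.47; 42% | 0.41; 46% |
| 0.63 SD | 0.44; 30% | 0.315; 21% | 0.19; 13% |

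The share of the effect removed is ρ·d_c/0.63: 15% at the mildest shifted setting (0.3 × 0.315/0.63) and 70% at the strongest (0.7 × 0.63/0.63). A simulation of all nine settings with 22 and 23 infants per arm gave the same adjusted effects and power within about 2 percentage points. Missed cord bloods would reduce the 45 further.

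**4. Does reading baseline as maternal close the gap?** For prenatal entry it gives a genuine pre-randomisation value, although in another person. For postnatal entry it leaves infants of non-nursing mothers with nothing. No reading gives a pre-randomisation value for all 90.

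**The case against.** The strongest reply is that Section 5.1 never says the baseline is the infant's. Section 4.2.1.1 schedules a maternal sample that it calls baseline, Section 4.2.2.2 samples nursing mothers at enrolment, and Section 3.5 says baseline procedures are complete before randomisation. That is fair, and these are the samples the fix relies on. But Section 4.2.1.2 gives the same label to cord blood. Section 4.2.2.2 lists the maternal draw after randomisation and dispensing, without fixing the order. The non-nursing gap also remains.

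A reader might infer three stronger things that the documents do not support.

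- *That every postnatal infant will be dropped.* This depends on complete-case fitting, which Section 5.1 does not prescribe. Section 4.6 calls for intent-to-treat, and Section 5.1 allows a stratified analysis in which the two routes need not share a covariate. Missing-covariate rules are also often left to an analysis plan. In addition, infants randomised close to the 182-day limit may have their 6-month sample near randomisation, although the protocol treats that visit as follow-up.
- *That the 85% is a miscalculation.* It reproduces, and it takes no credit for a covariate.
- *That IL1-beta is attenuated like DHA.* Section 2.2.3 speaks of fatty acids only; nothing in the documents shows a shift of IL1-beta in cord blood.

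One might also object that "The randomization method will be stratified by TrialNet study site" while Section 5.1 names no site term. That is a separate and minor matter, which this point does not rest on.

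Finally, the sample size was set by recruitment and the primary outcome is feasibility. This limits the weight of any power figure, but not of a biased estimate for a go/no-go criterion.

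**Conclusion.** The concern stands in this form: Section 5.1 fixes a baseline-adjusted model, and the schedule offers no valid baseline for it across the cohort. Following the model with the infant sample that the protocol itself calls baseline means conditioning on a post-treatment value in one entry route and having no covariate in the other. This goes beyond a detail left for later, because the prescribed model and the prescribed samples do not fit together.

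The size depends on complete-case fitting and on the assumed correlations and cord shifts. If treatment has not shifted the covariate, the cost is the lost half of the sample, partly recovered by the covariate. If it has, estimate and power both fall, and the bias is toward zero provided that the shift and the final effect have the same direction and ρ is positive. For DHA the protocol's own background supports a shift, though not its size. For IL1-beta it is conjecture.

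**What to change.** In Section 5.1, compare all randomised infants with treatment and entry route in the model. Allow as covariate only a value drawn before the first dose:

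- prenatal entry: the pregnant mother's pre-randomisation sample;
- postnatal entry: the nursing mother's enrolment sample, if drawn before the first dose.

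Fit the covariate within entry route, with a missing indicator so that no infant is dropped. State that cord-blood DHA and IL1-beta, and the sample taken at infant enrolment from mothers who entered in pregnancy, are post-randomisation values and are not covariates. In Section 4.2.1.2, stop calling the cord fatty acid and mediator levels baseline; the label for islet autoantibodies can stay.

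The cost is wording only, since every sample named is already scheduled. The drawback is that a maternal value will predict the infant's later level less well than a true infant baseline would have done. The comparison of all 90 nevertheless keeps the 84-85% power at 0.63 SD without relying on any covariate.

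### Randomisation is stratified by site, but the ANCOVA for Objectives 4 and 5 does not include site; if sites differ, the test is somewhat conservative

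*Protocol*

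**What the plan says.** On allocation, Protocol section 3.5 states: "The randomization method will be stratified by TrialNet study site". It names no other stratum and gives the purpose: "This approach ensures that the treatment groups will be approximately balanced within each site". The ratio is about 1:1: "Participants will be randomized, in approximately equal numbers, to the two arms of the study".

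On analysis, section 5.1 gives the same method for Objectives 4 and 5, a "t-test of treatment effect in an Analysis of Covariance (ANCOVA) model adjusted for the baseline level of each measure". After the list of objectives it adds entry pathway: "All analyses will be stratified according to whether the participant was entered into the study prenatally (i.e. during pregnancy) or was entered after birth". The means is left open between two options: "This adjustment will be conducted using an additional factor in a regression model or through a stratified-adjusted analysis".

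The comparative model as written therefore contains treatment, baseline and entry pathway. Section 5.1 mentions sites only for Objective 1, where accrual is averaged over them. Section 5.2 states 85% power for a difference of 0.63 SD at two-sided 0.05 with 90 participants and does not mention site.

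**The concern.** When arms are balanced within site, differences between sites cancel out of the treatment comparison, so the true variance of the estimated difference contains almost no between-site component. A model without site still counts that component as residual noise. Its standard error is then larger than the real sampling variability of the estimate.

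The protocol is not silent here. It writes out the adjustment terms and includes a factor that was not used in the randomisation (entry pathway), but leaves out the one that was. Some site variation is plausible, because DHA level depends on diet and feeding.

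At stake is precision in the two biomarker comparisons, which have about 45 participants per arm. Validity is not at stake.

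**Working it through.** **Inputs from the protocol.** 90 participants, 9 sites, an average of 10 per site (section 5.2); about 1:1 allocation, stratified by site (section 3.5); effect 0.63 SD, two-sided 0.05, stated power 85% (section 5.2).

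**Assumed.** The share of outcome variance that lies between sites after baseline and entry pathway are adjusted for, written ρ. The protocol does not give it. Range used: 0 to 0.20.

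**Step 1: reproduce the stated power.** With residual SD 1 and 45 per arm, SE = √(2/45) = 0.2108, and 0.63/0.2108 = 2.988. Normal approximation: Φ(2.988 − 1.960) = 84.8%. Noncentral t with 88 df: 84.0%. The stated 85% reproduces as a plain two-group comparison with no site term.

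**Step 2: what a site term does to the standard error.** With even balance within sites, the true SE is close to √(2/45) × √(1 − ρ). A model without site reports about √(2/45). The overstatement is therefore about 1/√(1 − ρ).

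| ρ | True SE | Reported ÷ true (formula) | Reported ÷ site-adjusted (simulated) |
|---|---|---|---|
| 0 | 0.2108 | 1.000 | 1.000 |
| 0.05 | 0.2055 | 1.026 | 1.024 |
| 0.10 | 0.2000 | 1.054 | 1.050 |
| 0.20 | 0.1886 | 1.118 | 1.109 |

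**Step 3: type I error and power by simulation.** 40,000 simulated trials per setting; 9 sites of 10, split 5/5; total residual SD 1 after baseline; an entry-pathway factor in both models; 8 site indicators added in the second.

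| ρ | Type I error, no site | Power, no site | Power, site added |
|---|---|---|---|
| 0 | 5.0% | 83.7% | 83.6% |
| 0.02 | 4.8% | 84.1% | 84.5% |
| 0.05 | 4.4% | 84.8% | 85.8% |
| 0.10 | 4.1% | 85.4% | 87.6% |
| 0.20 | 3.1% | 86.7% | 90.7% |

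With site in the model, type I error stays at about 5%. Uneven site sizes, from 26 down to 2, give nearly the same figures. An analytic check for the site-adjusted model (noncentral t, 78 df) gives 83.9%, 85.7%, 87.5% and 91.0% at ρ = 0, 0.05, 0.10 and 0.20.

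**Step 4: allow for imbalance after randomisation.** Section 3.7.1 withdraws families who were randomised in pregnancy if the infant proves ineligible on HLA type, and section 1.2.2 expects about half of entries to be prenatal. The split within a site need not stay 5/5. Assume 12 randomised per site (6/6), half of them prenatal, and 35% of those withdrawn. That leaves on average 12 − 6 × 0.35 = 9.9 per site, or about 89 in all. The 35% is an assumption; the protocol gives no figure.

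| ρ | Change in power from adding site |
|---|---|
| 0 | −0.9 point (83.3% to 82.4%) |
| 0.05 | +0.4 point (84.2% to 84.6%) |
| 0.10 | +1.8 points |
| 0.20 | +4.0 points |

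Repeat runs of this setting put the cost at ρ = 0 between about 0.4 and 0.9 point.

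**The case against.** The strongest reply has four parts.

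*No stated figure is wrong.* A reader might infer that the 85% power in section 5.2 is overstated, or that ignoring the randomisation stratum inflates false positives. Neither follows. The 85% reproduces without a site term, and at a fixed total SD the power of the model as written rises slightly with ρ. Type I error is at or below 5%. What is forgone is power beyond the plan. This stands.

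*The harm is conditional.* It needs site differences that remain after baseline and pathway adjustment, and the protocol quantifies none. Baseline will absorb part of any stable site difference, and use of core laboratories (section 9.2.3) limits assay differences. This also stands, and so it cannot be said outright that the intervals will be too wide. Baseline may absorb less than usual, however. For infants entering after birth, sections 4.2.2.1 and 4.2.2.2 schedule no fatty acid or inflammatory mediator sample from the infant before the 6-month visit. For prenatal entrants, that sample depends on cord blood being available.

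*Adding site is not entirely free.* Step 4 shows that it is close to neutral when site effects are small. This stands.

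*It belongs in the statistical analysis plan.* Section 5.1 never says that its terms are exhaustive, and a plan not shown here may add site. This stands in part: the protocol does not exclude site. But it does write out a model with named adjustments, and the randomisation stratum is not among them.

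**Conclusion.** The point holds as a minor, conditional one. The analysis specified for Objectives 4 and 5 does not include the only factor on which randomisation is stratified. If sites differ after adjustment, inference is conservative: at assumed residual site shares of 5%, 10% and 20%, the reported standard error is about 2%, 5% and 11% too large. Including site would then gain about 1, 2 and 4 points of power, or about 0.4, 2 and 4 points if withdrawals unbalance the sites. If sites do not differ, the omission costs nothing.

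These figures rest on the assumed site shares, on residual SD 1 after baseline adjustment and, for the second set, on the assumed 35% withdrawal rate. The primary outcome is feasibility and the sample size was set by recruitment, so the effect on the pilot's main conclusions is small.

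**What to change.** In section 5.1, add TrialNet site to the ANCOVA for Objectives 4 and 5, alongside baseline and entry pathway. State its form, either a fixed effect or a random intercept, together with any rule for pooling very small sites, and settle this before unmasking so that the choice cannot depend on the treatment comparison.

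The cost is one phrase in the protocol and 9 − 1 = 8 degrees of freedom with fixed effects. If sites do not differ, the loss is about 0.1 point of power with even balance and at most about 1 point with the imbalance in Step 4. No extra participants, visits or samples are needed, and section 5.2 can stay as it is.
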